1.4 RANDOMISATION AND BLINDING

As participants are confirmed to be eligible for the study, they are assigned a single unique identifier across the study.

At screening, participants receive a unique screening number using the letter S and a number ranging from 001 to 999. Participants who fail screening and are not enrolled are not included in the final database but recorded in a separate screening log. The failure details are documented in the 'participants' file.

Participants are assigned to 1 of 2 treatment groups. Allocation of each participant to a given treatment group is determined from a randomization list (to be linked to the unique identifier) prepared prior to study start by SGS Life Sciences Secure Data Office using SAS® software (SAS Institute Inc., Cary, NC, USA).

The randomization list is generated using randomly permuted blocks and is not stratified. Participants are randomised 3:2 to receive either MVA-NP+M1 or saline Placebo, with total enrolment of approximately 155 participants at an allocation of 93 to 62. The challenge period will include up to approximately 80 participants in the MVA-NP+M1 vs up to approximately 54 participants in the saline Placebo group.

The pharmacist or an appropriate qualified member of the study staff, who is unblinded to treatment and assigned by the principal investigator, prepares the study vaccine that corresponds to the assigned participant randomization number. The recruiters calling vaccinated participants back to quarantine, are also blinded to the study status, therefore the Statistical Centre supplies the list of participants to be called to undergo challenge and quarantine.

The randomization list is retained by SGS Life Sciences Secure Data Office until the end of the study (database lock). One copy of the randomization list is sent in a sealed envelope to the site pharmacist before the start of the study.

One copy of code breaking envelopes is made available to the clinical site, to be used only in case of emergency. The reason for unblinding is documented in the appropriate section of the eSource. Participants who are unblinded for any reason during their participation in the study are not to be replaced and are withdrawn immediately from the study (except for safety monitoring).

1.5 INTERIM ANALYSIS

No formal interim analyses are planned. Topline results will be presented before database lock, with unblinding at group level only. TLFs to be included in this analysis are identified in section 8.

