5.5 RANDOMIZATION AND BLINDING

As participants are confirmed to be eligible for the study, they will be assigned a single unique identifier across the study.

At screening, participants receive a unique screening number using the letter S and a number ranging from 001 to 999. Participants who fail screening and are not enrolled will not be included in the final database but will be recorded in a separate screening log. The failure details will be documented in the 'participants' file.

Participants will be assigned to 1 of 2 treatment groups. Allocation of each participant to a given treatment group will be determined from a randomization list (to be linked to the unique identifier) prepared prior to study start by SGS Life Sciences Secure Data Office using SAS® software (SAS Institute Inc., Cary, NC, USA).

The randomization list will be generated using randomly permuted blocks and will not be stratified. Participants will be randomised 3:2 to receive either MVA-NP+M1 or saline Placebo, with total enrolment of 155 participants at an allocation of 93 to 62. Each grouping of up to 20 participants will be given a specific date, approximately three weeks apart, to enter the quarantine facility in order to be challenged. If more than 20 participants from a vaccination group are eligible and available for challenge, participants who are willing to enter at another date will be enrolled with a later cohort to reach the correct allocation of up to 20 participants per challenge. The challenge period will include up to approximately 80 participants in the MVA-NP+M1 vs up to approximately 54 participants in the saline Placebo group.

The pharmacist or an appropriate qualified member of the study staff, who is unblinded to treatment and assigned by the principal Investigator, will prepare the study vaccine that corresponds to the assigned participant randomization number. The recruiters calling vaccinated participants back to quarantine, will also be blinded to the study status, therefore the Statistical Centre will supply the list of participants to be called to undergo challenge and quarantine.

The randomization list will be retained by SGS Life Sciences Secure Data Office until the end of the study (database lock). One copy of the randomization list will be sent in a sealed envelope to the site pharmacist before the start of the study. Throughout the study conduct, the monitor needs to check the completeness and status of

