9. STATISTICAL METHODS

9.1 STATISTICAL ANALYSIS

No formal interim analyses are planned for this trial.

Statistical analyses will be performed by a qualified vendor under the supervision and responsibility of the Sponsor, using SAS® (SAS Institute Inc., Cary, NC, USA; version 9.2 or higher) and/or Phoenix™ WinNonlin® (Pharsight Corporation, Palo Alto, CA, USA; version 6.1 or higher). Unscheduled interim analyses may be performed at the request of the IDMC to monitor the safety of the investigative vaccine throughout the study (also Section 5.7). Details will be described in a separate IDMC charter.

The following populations will be considered for analysis:

- intent-to-treat (ITT) population, defined as all randomized participants who received the challenge inoculation, according to the assigned (randomized) treatment group

- per-protocol (PP) population, consisting of a subset of the ITT population without any major protocol deviations and including those participants who remain in the quarantine facility for the full extent of the challenge phase
- safety population, consisting of all participants vaccinated in the vaccine phase, according to the vaccination actually received
- challenge safety population, which includes all of those in the above defined ITT, according to the vaccination actually received.

Unless specified otherwise, the ITT population will be used for efficacy and immunogenicity analysis. The safety populations will be used for safety/tolerability analysis and analysis of demographics.

All statistical methods shall be detailed in a Statistical Analysis Plan (SAP) to be issued by SGS statistical team and finalized before database lock. The SAP will be approved by the Vaccitech Ltd statistical consultant.

The final efficacy analysis will be performed once all participants have completed 27 days from the time of inoculation (Day 28 post-challenge) or 6 months post-vaccination, whichever is last.

For continuous variables, descriptive statistics will include mean, standard deviation (SD), median, minimum, maximum, and range. For categorical variables, descriptive statistics will include frequencies and percentages.

9.1.1 *Baseline Characteristics*

For all participants who undergo vaccination, descriptive statistics will be provided per vaccination group for demographic (e.g. age, height, weight, BMI, race, sex) and other initial participant characteristics (physical examination, medical and surgical history, concomitant diseases).

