2.1.3 Inferential statistics

All statistical comparisons will be made using two-sided tests at the 0.05 significance level unless specifically stated otherwise. As this is a proof-of-concept study, no correction method for multiple testing is foreseen. P-values should thus be interpreted accordingly.

Difference between MVA-NP+M1 and placebo in AUC (qPCR vAUC - primary analysis, culture vAUC, overall, local and general SSC AUC) and peak viral shedding/symptoms will be analysed using a Mann-Whitney U test. Additionally, adjusted difference between MVA-NP+M1 and placebo in AUC (qPCR vAUC, culture vAUC and overall SSC AUC) will be analysed using an ANCOVA model with treatment, sex, time since vaccination (see section 4.6.2) and challenge cohort as covariates.

Difference between MVA-NP+M1 and placebo in attack rate and virologically confirmed ILI will be analysed using a Fisher exact test.

Time to parameters will be analysed using Kaplan-Meier time to event analysis, with a log-rank test to compare MVA-NP+M1 and placebo.

Difference between MVA-NP+M1 and placebo in total days of fever will be tested using a zero inflated Poisson model.

Difference between MVA-NP+M1 and placebo in total mucus production will be tested with a t-test. Normality will be tested using a Shapiro-Wilk test. In case normality or homogeneity of variances assumption are not valid, a Mann-Whitney U test will be used.

Difference between MVA-NP+M1 and placebo in overall SSC changes from baseline will be analysed using a mixed model for repeated measurements (MMRM). The

	Statistical Analysis Plan	
FLU010	Final analysis	Final 3.0 of 15JUN2020

model will include treatment, sex, challenge cohort, timepoint and treatment by timepoint interaction terms as fixed effects, with baseline value and time since vaccination (see section 4.6.2) as covariates. Within-subject correlation will be modeled by assuming an unstructured (UN) covariance matrix for the error terms. If the model does not converge upon using UN, the following covariance structures will be tested for convergence (in order): heterogeneous Toeplitz (TOEPH), heterogeneous autoregressive first order (ARH(1)), heterogeneous compound symmetry (CSH), Toeplitz (TOEP), autoregressive first order (AR(1)) and compound symmetry (CS).

A similar MMRM model will be used for viral load (qPCR and culture) actual values, without the baseline covariate.

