5. GENERAL METHODOLOGY

5.1 ANALYSIS SETS

5.1.1 *Analysis sets*

The following analysis sets will be considered in the statistical analysis:

All randomised subjects subjects who were *randomised* into this study set (RND):

Safety analysis set (SAF) subjects who were *exposed* to the vaccine, according to the vaccine actually received

Intent-to-treat set (ITT) randomised subjects who received the challenge inoculation, according to randomised treatment group

Per-protocol set (PP) ITT subjects without any major protocol deviations impacting the primary endpoint and *remain in the quarantine facility for the full extent of the challenge phase*

Challenge safety set (CSAF) randomised subjects who received the challenge inoculation, according to actual treatment received

Programming notes:

- Randomised is defined as having a complete randomisation date in the database or any information to confirm randomisation.
- Being exposed to the vaccine is defined as having a complete exposure date in the database or any information to confirm vaccination.
- If a subject does not remain in the quarantine facility for the full extent of the challenge phase, this will be reported as a major protocol deviation.
- Major protocol deviations impacting the primary endpoint will be flagged as such in the database.

Unless stated otherwise, the ITT will be used for the efficacy and immunogenicity tables, listings and figures. The SAF will be used for the safety and general characteristics tables, listings and figures. The primary efficacy analysis will be repeated on the PP and CSAF (only in case PP and/or CSAF differ from ITT).

5.1.2 *As planned versus as actual analysis*

For analyses done on the safety analysis set and challenge safety set, the actual treatment of the subject will be considered.

For all other analyses, the planned treatment will be used.

	Statistical Analysis Plan	
FLU010	Final analysis	Final 3.0 of 15JUN2020

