8. LIST OF TABLES AND LISTINGS

Topline TLFs are flagged as 'TL'.

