8.1 TABLES

GENERAL CHARACTERISTICS

14.1.1.1	Analysis Sets	RND	
14.1.1.2	Subject Disposition	SAF	TL
14.1.1.3	First and Last Contact in the Study	RND	
14.1.1.4	Analysis Phase Duration	SAF	
14.1.1.5	Major Protocol Deviations	SAF	
14.1.2.1	Demographic Data	SAF	TL
14.1.2.2	Vaccine Administration, Overall and by Vaccinated Cohort	SAF	
14.1.2.3	Influenza Challenge, Overall and by Challenge Cohort	SAF	
14.1.2.4	Time Between Vaccination and Challenge	SAF	

EFFICACY

14.2.1.1.1	qPCR Viral Shedding - qPCR vAUC (Primary Endpoint)	ITT	TL
14.2.1.1.2	qPCR Viral Shedding - qPCR vAUC (Primary Endpoint) - Per Protocol Set	PP	TL
14.2.1.1.3	qPCR Viral Shedding - qPCR vAUC (Primary Endpoint) - Challenge Safety Set	CSAF	TL
14.2.1.1.4	qPCR Viral Shedding - qPCR vAUC (Primary Endpoint) - Multiple Imputation	ITT	
14.2.1.1.5	qPCR Viral Shedding - qPCR vAUC (Primary Endpoint) - ANCOVA	ITT	TL
14.2.1.1.6	qPCR Viral Shedding - qPCR vAUC (Primary Endpoint) - ANCOVA - Multiple Imputation	ITT	
14.2.1.2	qPCR Viral Shedding - qPCR Attack Rate (Secondary Endpoint)	ITT	
14.2.1.3	qPCR Viral Shedding - Rate of Virologically Confirmed Influenza-like Illness (Secondary Endpoint)	ITT	
14.2.1.4	qPCR Viral Shedding - Time to Start of Viral Shedding (qPCR) (Secondary Endpoint)	ITT	
14.2.1.5	qPCR Viral Shedding - Peak Viral Shedding (qPCR) (Secondary Endpoint)	ITT	
14.2.1.6	qPCR Viral Shedding - Time to Peak of Viral Shedding (qPCR) (Secondary Endpoint)	ITT	
14.2.1.7	qPCR Viral Shedding - Time to Cessation of Viral Shedding (qPCR) (Secondary Endpoint)	ITT	
14.2.1.8	qPCR Viral Shedding - Duration of Viral Shedding (qPCR) (Secondary Endpoint)	ITT	
14.2.1.9	qPCR Viral Shedding - log qPCR Actual Values Over Time	ITT	TL
14.2.1.10	qPCR Viral Shedding - log qPCR Mixed Model for Repeated Measures	ITT	TL
14.2.2.1.1	Culture Viral Shedding - Culture vAUC (Secondary Endpoint)	ITT	
14.2.2.1.2	Culture Viral Shedding - Culture vAUC (Secondary Endpoint) - ANCOVA	ITT	
14.2.2.2	Culture Viral Shedding - Culture Attack Rate (Secondary Endpoint)	ITT	

	Statistical Analysis Plan	
	FLU010	Final analysis

14.2.2.3	Culture Viral Shedding - Time to Start of Viral Shedding (Culture) (Secondary Endpoint)	ITT	
14.2.2.4	Culture Viral Shedding - Peak Viral Shedding (Culture) (Secondary Endpoint)	ITT	
14.2.2.5	Culture Viral Shedding - Time to Peak of Viral Shedding (Culture) (Secondary Endpoint)	ITT	
14.2.2.6	Culture Viral Shedding - Time to Cessation of Viral Shedding (Culture) (Secondary Endpoint)	ITT	

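### By-arm topline results, including the primary test, are shown before database lock, with no prior freeze of the efficacy data, per-protocol flags or SAP

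*SAP*

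**What the plan says.** SAP 1.5 opens with "No formal interim analyses are planned" and continues: "Topline results will be presented before database lock, with unblinding at group level only". The content of the topline is set by a TL mark in the output lists of SAP 8. Among the marked tables is "qPCR Viral Shedding - qPCR vAUC (Primary Endpoint) - Per Protocol Set".

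The protocol does not mention a topline analysis. On custody of the codes, section 5.5 says: "The randomization list will be retained by SGS Life Sciences Secure Data Office until the end of the study (database lock"). SAP 1.4 repeats this. Protocol 5.4 has the site monitor complete drug accountability after lock, when treatments have been unblinded. On timing, Protocol 9.1 says "The final efficacy analysis will be performed once all participants have completed 27 days from the time of inoculation", or at 6 months after vaccination if that is later. The same section requires the SAP to be final before lock.

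On the per-protocol set, SAP 5.1.1 says: "Major protocol deviations impacting the primary endpoint will be flagged as such in the database". SAP 6.1, the place for departures from the protocol made before lock, has only the entry NAP.

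**The concern.** Blinding until lock protects more than the participants' assessments. It lets a sponsor show that every query resolution, deviation classification and change to the analysis plan was made without knowing which way it would move the result. Under the SAP's sequence, the comparison of the two arms on the primary endpoint is shown while all three can still change. If the final vAUC result then differs from the topline, or per-protocol membership differs, nothing in the documents would let the sponsor show that the change was made blind. At stake is the credibility of the primary comparison and its per-protocol repeat.

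**Working it through.** No arithmetic applies: the point concerns the order of events. I traced the topline marks and then set the relevant sections against each other.

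1. **What the topline contains.** SAP 8.1 lists six tables for the primary qPCR vAUC, and four are marked TL: 14.2.1.1.1 (ITT), 14.2.1.1.2 (per-protocol), 14.2.1.1.3 (challenge safety) and 14.2.1.1.5 (ANCOVA). The two multiple-imputation tables, 14.2.1.1.4 and 14.2.1.1.6, are not. Under SAP 5.1.1 the second and third are run only if those sets differ from ITT. Also marked are the log qPCR values over time (14.2.1.9), the qPCR MMRM (14.2.1.10), and the overall symptom-score AUC by Mann-Whitney and ANCOVA (14.2.3.1.1 and 14.2.3.1.3). The primary p-value is therefore in the package.

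2. **What is still open when it is shown.**

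| Item | When the documents close it | State at topline |
|---|---|---|
| qPCR, culture and symptom data | Lock follows once data are judged clean (Protocol 12.6) | Editable |
| Deviation flags for the per-protocol set | No date; a field in the database (SAP 5.1.1) | Must exist, but can be revised until lock |
| SAP text | Before lock (Protocol 9.1) | Can be revised |
| Topline data cut | Mentioned in SAP 5.2.1, not defined | Unknown |
| 5% missing-data trigger (SAP 5.3.1) | Rule fixed | Its input data can change |
| VIF above 10 drops challenge cohort (SAP 2.1.3) | Rule fixed | Its input data can change |
| ELISpot subsets (SAP 2.2.4) | Both always reported; none is topline | No choice to make |

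3. **Consistency with the protocol.** By-arm tables need treatment codes. Protocol 5.5 and SAP 1.4 keep the list in the Secure Data Office until lock, and Protocol 5.4 puts unblinding after lock. SAP 1.5 puts a group-level unblinding before it. SAP 6.1 does not record the difference.

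4. **Safeguards described.** I found no data freeze or snapshot before the topline, no sign-off of analysis-set flags, no list of who sees the results, no separate unblinded team, and no requirement that the SAP be final before the topline.

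**The case against.** The case on the other side is substantial, and most of it stands.

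- Unblinding is at group level, and no listing in SAP 8.2 is marked topline. Someone who knows the p-value but not a participant's arm generally cannot tell which way a given query will move it. The Secure Data Office could support group-level output without releasing the list. A reader might infer that group-level masking gives no protection; that is too strong.
- The primary test leaves little to steer. It is ITT, so no deviation flag enters it. The endpoint is a laboratory measurement. The trapezoid, missing-value, detection-limit and rounding rules are written down, and SAP 5.3.5 rules out outlier detection.
- A reader might count the VIF rule, the 5% trigger and the ELISpot subsets as free choices. They are not: the first two are numeric rules and both subsets are always shown.
- A reader might infer that the protocol forbids any efficacy analysis before follow-up ends. Protocol 9.1 speaks of the final efficacy analysis, and the SAP does not say that the topline precedes the end of follow-up.
- Some controls exist. Changes following monitoring leave an audit trail in the eSource system (Protocol 12.3), a topline cut-off is envisaged, and the procedures cited in SAP 1.7 may cover more than can be seen here.

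Three things remain. First, group-level output is not fully masked. Descriptive statistics include the minimum and maximum (SAP 5.4.1), and a by-arm Kaplan-Meier plot of time to start of shedding is topline. Someone with blinded participant-level data could match an unshared extreme value or event time to an arm. SAP 1.7 also requires independent programming of the primary tables, so more than one person probably handles codes before lock, and nothing separates them from cleaning or per-protocol decisions. Second, an audit trail shows that a value changed, not whether the person who changed it knew the result. Third, neither masking nor the trail covers revision of the per-protocol flags as a group, or of the SAP.

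**Conclusion.** The concern holds as a should-fix. The SAP states a sequence, rather than merely omitting detail, in which efficacy data, per-protocol flags and SAP text can change after the by-arm primary result has been shown. That sequence departs from the protocol's order of lock and unblinding without being recorded as a departure. The exposure is small for the ITT Mann-Whitney test and larger for the per-protocol repeat, whose membership rests on a judgement about which deviations bear on the primary endpoint. The size cannot be quantified from the documents.

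Two stronger readings should be resisted. A reader might infer that the changes in SAP 2.0 (which narrowed the per-protocol exclusions) or SAP 3.0 (which altered the T-cell rules at the sponsor's request) were informed by results. The documents do not date the topline, so they do not support this, and they show no decision made with the answer known. A reader might also treat the topline as an interim look that calls for an alpha adjustment. It carries no stopping option, so none follows, and the SAP describes the trial as proof-of-concept.

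The conclusion assumes that no unseen procedure already imposes a freeze. If one does, the remedy is to cite it in SAP 1.5.

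**What to change.** Rewrite SAP 1.5 so that, before any by-arm output is produced:

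- the qPCR, culture, symptom-score, dosing and deviation data, and the per-protocol and challenge safety flags, are frozen and signed off;
- the topline cut-off is defined;
- the SAP is final for every topline analysis.

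Safety follow-up and later laboratory results such as ELISpot, which SAP 2.2.1 says may not be ready even for the final analysis, may stay open.

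Apply the VIF and 5% missing-data rules mechanically to the frozen data. The VIF cannot be settled before codes are used, because the code in SAP 9.1 includes treatment. That code also enters challenge cohort as a plain regressor, while the ANCOVA treats it as a class effect, so the SAP should state the coding in advance.

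Keep anyone with access to treatment codes out of cleaning and per-protocol decisions. Log every later change to frozen data. If such a change affects the primary result, report that result from both the freeze and the final lock. Reconcile SAP 1.4, 1.5 and 6.1 with Protocol 5.4 and 5.5.

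The cost is SAP wording and a staged lock; the topline may come slightly later.

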1.6 SOFTWARE

SAS version 9.4 or later will be used for programming.

	Statistical Analysis Plan	
FLU010	Final analysis	Final 3.0 of 15JUN2020

1.7 VALIDATION MODEL

SGS Life Sciences (SGS LS) – Clinical Research statistics (STAT) standard operating procedures (SOPs) and work instructions (WIs) as effective at the project start will be followed throughout the project, provided the applicable regulatory requirements are still met.

The primary endpoint tables will be validated according to Model C: review by an independent person and independent programming. All other analysis tables/figures/listings will be validated according to Model B: review by an independent person (see SOP.STAT.020).

	Statistical Analysis Plan	
FLU010	Final analysis	Final 3.0 of 15JUN2020

2. EFFICACY AND IMMUNOGENICITY ANALYSES

2.1 EFFICACY

2.1.1 *Available data*

Nasal swabs for influenza virus are collected twice a day (at least 8 hours apart) from Day 2 to Day 10 following intranasal challenge, which are tested for influenza using quantitative polymerase chain reaction (qPCR) and culture. Culture is only done for positive qPCR samples.

The following symptoms of influenza-related infection will be collected twice a day (except for lymphadenopathy, which will be collected once a day only) from Day 1 to Day 11 of challenge on a symptom score card (SSC):

- Local symptoms:
 - Nose (4): nasal congestion (blocked nose), runny nose, sneezing frequency, sinus pressure/pain or facial pain
 - Throat (2): sore throat, difficulty swallowing
 - Eyes (3): tearful/watery eyes, painful eyes, aversion to light
 - Chest/respiratory (3): dry cough, productive (wet) cough, difficulty breathing/tight chest
- General symptoms:
 - Gastrointestinal (4): nausea, stomach ache, vomiting, diarrhoea
 - Body/systemic (12): dizziness, head congestion, headache, muscle aches, feverish, chills or shivering, lack of appetite, felt cold, sweating, tiredness/weakness, sleeping more than usual, lymphadenopathy
 - The following symptoms will only be questions if at least 2 other symptoms with grade 2 or higher are present: nausea, stomach ache, vomiting, diarrhoea, tiredness/weakness, sleeping more than usual.

Each symptom's severity is graded from 0 (absent) to 3 (grade 3 - severe).

Additionally, the SSC also contains the question whether the subject feels well enough to go to work today (yes/no).

Oral body temperature is assessed daily during confinement as part of the vital signs evaluation. During this same period, tissue collection is planned daily to measure daily mucus production.

	Statistical Analysis Plan	
FLU010	Final analysis	Final 3.0 of 15JUN2020

2.1.2 *Endpoints and derivation rules*

2.1.2.1 *PRIMARY ENDPOINT*

Primary endpoint is the viral area under the curve (vAUC) based on the qPCR values. AUC will be calculated using the linear trapezoidal rule, by summing all individual trapezoids, which will be calculated as follows:

$$AUC_{t_i-t_{i+1}} = 1/2 * (L_i + L_{i+1}) * (t_{i+1} - t_i).$$

Where:

- L_i is the log-transformed viral load concentration at time point t_i .
- All time points (including unscheduled time points) from day 2 to day 10 will be considered.
- AUC will be calculated in hours, using actual datetimes of qPCR assessments.
- AUC will be rounded as detailed in section 5.3.4.
- Missing values will be imputed as detailed in section 5.3.1.

2.1.2.2 *SECONDARY ENDPOINTS*

The following secondary endpoints will be derived:

- Attack rate: a successful attack is defined as having at least two positive swabs (derived for both qPCR and culture) within the timespan of two consecutive days
- Time to start of viral shedding (hours) = (datetime of first of two positive swabs within 2 consecutive days - challenge datetime)/(60*60)
 - Time will be rounded as detailed in section 5.3.4
 - All time points (including unscheduled time points) from day 2 to day 10 will be considered.
 - Subjects not having at least two positive swabs (within 2 consecutive days) will be censored on the last viral load assessment
 - This endpoint will be derived for both qPCR and culture
- Peak viral shedding = highest viral load concentration
 - All time points (including unscheduled time points) from day 2 to day 10 will be considered.
 - Subjects not having at least two positive swabs (within 2 consecutive days) will be excluded from this analysis (peak viral shedding not calculated).
 - This endpoint will be derived for both qPCR and culture

	Statistical Analysis Plan	
FLU010	Final analysis	Final 3.0 of 15JUN2020

- Time to peak of viral shedding (hours) = (datetime of highest viral load concentration - challenge datetime)/(60*60)
 - Time will be rounded as detailed in section 5.3.4
 - All time points (including unscheduled time points) from day 2 to day 10 will be considered.
 - In case of identical peak values, the first in time will be considered.
 - Subjects not having at least two positive swabs (within 2 consecutive days) will be censored on the last viral load assessment
 - This endpoint will be derived for both qPCR and culture
- Time to cessation of viral shedding (hours) = (datetime of first negative swab following the last positive swab - challenge datetime)/(60*60)
 - Time will be rounded as detailed in section 5.3.4
 - All time points (including unscheduled time points) from day 2 to day 10 will be considered.
 - Subjects not having at least two positive swabs (within 2 consecutive days) will be excluded from this analysis (time to cessation not calculated).
 - An event is defined as having two consecutive negative swabs not followed by a positive swab. Subjects without an event will be censored on the last viral load assessment.
 - This endpoint will be derived for both qPCR and culture
- Duration of viral shedding (hours) = (datetime of first negative swab following the last positive swab - datetime of first positive of two positive swabs within 2 consecutive days)/(60*60)
 - Duration will be rounded as detailed in section 5.3.4
 - All time points (including unscheduled time points) from day 2 to day 10 will be considered.
 - Subjects not having at least two positive swabs (within 2 consecutive days) will be excluded from this analysis (duration of viral shedding not calculated).
 - The end of viral shedding is defined as two consecutive negative swabs not followed by a positive swab. If this does not occur, the end of viral shedding will be set to the last viral load assessment.
 - This endpoint will be derived for both qPCR and culture
- vAUC based on culture values will be derived following the same rules as for the primary endpoint

	Statistical Analysis Plan	
FLU010	Final analysis	Final 3.0 of 15JUN2020

- Rate of virologically confirmed ILI: virologically confirmed ILI is defined as having a positive swab and a respiratory or flu-like symptom occurring on two consecutive days
 - A positive swab is defined as a positive qPCR.
 - All time points (including unscheduled time points) from day 2 to day 10 will be considered.
 - Positive swab and flu-like symptom have to occur on the same two consecutive days.
 - Respiratory or flu-like symptom can be any of the following signs or symptoms collected on the SSC: runny nose, sneezing frequency, sinus pressure/pain or facial pain, sore throat, difficulty swallowing, teary/watery eyes, painful eyes, aversion to light, dry cough, productive (wet) cough, difficulty breathing/tight chest, feverish, chills or shivering, sweating, lymphadenopathy
- Overall SSC AUC
 - AUC will be derived following the same rules as for the primary endpoint and rounded as detailed in section 5.3.4
 - SSC AUC will be calculated using the overall SSC score
 - Overall SSC score = arithmetic mean of all items
 - As lymphadenopathy is assessed only once a day, the value collected for that day will be used for both the AM and PM assessments in the calculation of SSC score.
 - Missing items will be handled as detailed in section 5.3.1

